Project title:

Effects of combined repetitive transcranial magnetic stimulation and treadmill training on gait performance in Parkinson's disease – a randomised controlled trial

NCT no: NCT02701647

Date of document: 22 Dec 2015

1. Project Title:

Effects of combined repetitive transcranial magnetic stimulation and treadmill training on gait performance in Parkinson's disease – a randomised controlled trial

2. Project Objectives:

There are three objectives in this research study:

1. To compare short- and long-term effects of 25Hz repetitive transcranial magnetic stimulation (rTMS) with 1Hz rTMS followed by treadmill training on their gait performance during single task and dual task conditions in people with Parkinson's disease (PD)
2. To compare short- and long-term effects of 1Hz with 25Hz rTMS followed by treadmill training on corticomotor excitation and intracortical inhibition in people with PD.
3. To explore whether combined rTMS and treadmill training can be transferred to enhancement of balance performance in people with PD

3. Scope and Background of Research:

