than this, the principal of activity dependent neuroplasticity suggests that motor learning has to be task specific (22). Therefore, application of rTMS before specific motor training may boost up the training effect. Yang et al (23) recently demonstrated that 12 sessions over 4 weeks of 5Hz rTMS and treadmill training compared with treadmill alone led to better improvement of walking and functional mobility performance accompanied with some positive changes in intracortical inhibition. This modulation of intracortical inhibition has also been shown after high intensity treadmill training (24). These findings are very intriguing but further randomised control trials with more sample sizes are warranted to minimise bias. In addition, it is uncertain if the rTMS stimulation protocol used in Yang et al study is optimal. The carry over effect has also not been examined.

Therefore, this research projects aim to determine a rTMS stimulation protocol that would optimise the beneficial effect of treadmill training in PD by comparing the 2 different stimulation frequency protocols i.e. 1Hz and 25 Hz. In addition, rTMS has been found to restore the intracortical inhibition in PD (23). The restoration of the cortical inhibition through rTMS may have therapeutic effect on the defective cortical-basal ganglia-cortical network in PD (8). The inhibitory signals are essential for optimal execution of motor program by inhibiting other inappropriate and competing circuits. As discussed earlier, the basal ganglia allow well-learned movement such as walking to be performed with less attention resources. Hence, it would be interesting to investigate if rTMS would enhance the automaticity of walking and thus better dual-task walking performance.

Last but not least, it will be interesting to investigate whether combined rTMS and treadmill training can be transferred to enhancement of balance performance in PD as treadmill training has been found to reduce fall rate in PD (33).

4. Research Methodology:

Study Design: A double-blinded randomised controlled trial

Participants

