Fifty-one participants with PD will be recruited with the following inclusion criteria for study part III: 1) Aged 40 to 70, 2) Diagnosed with idiopathic Parkinson's disease by a neurologist 3) Hoehn & Yahr Scale Stage II to III with stable medications usage 4) ability to walk independently with or without walking aids for 10 metres. The exclusion criteria are as follow: 1) severe comorbidity that may interfere with their ability to participate in the study (e.g. chronic obstructive airway disease, angina, congestive cardiac failure, and significant renal or liver disease, malignancy) 2) significant orthopaedic or rheumatological conditions or disorders of peripheral nervous system that may interfere with mobility or balance performance 3) Female subjects who are pregnant 4) Neurological disease other than PD 5) a score of less than 23 on the Mini-Mental State Examination 6) any auditory or visual impairment 7) History of neurosurgery 8) contraindication to TMS including personal or family history of seizure disorder, metal in the head, implants of medical devices such as cardiac pacemakers or medical pumps (Appendix 1). 9) Subjects with irrepressible tremor and/dyskinesia. Informed consent in accordance with the Declaration of Helsinki will be obtained from all participants and data collection will only be carried out after the approval of Hong Kong Polytechnic University Ethics Committee.

The sample size calculation is based the significant findings of the gait speed and cortical silent period reported by Yang et al. (23). A two-way repeated measures ANOVA design with between-subject group effect (3 levels) and within-subject time effect (4 levels) determines that fifteen subjects per group are required to achieve 85% power to test the interaction effect between group and time effect with a 5% significance level and the effect size is 0.4. By assuming 10% dropout rate, 17 subjects will be required per group.

Experimental protocol

Part I & II. Mapping study and reliability study

Measures of cortical excitability including resting motor threshold (RMT) and recruitment curves will be obtained with transcranial magnetic stimulation (TMS) for 10 healthy subjects for study part I to identify the optimal site for TMS stimulation of the tibialis anterior (TA) muscles.

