participants will wear a safety harness without body weight support during walking on the treadmill to prevent falls. The maximum tolerated walking speed was determined before training session. Half of the maximum speed will be used for a 5-minute warm up; the training walking speed will be increased by increments of 0.6km/h every 5 minutes. When the belt speed is increased to the highest speed at which the subject could walk safely and without stumbling. This maximum – achieved belt speed will be maintained for 5 minutes and then followed by 0.6km/h decrements. The subject will maintain this speed for the rest of the treadmill session for 15 minutes. If subject is unable to maintain this speed, it will be reduced by 0.6km/h in the next phase. If subject is able to maintain this reduced speed for 5 minutes, the speed will increase during the next phase by 0.6km/h. The treadmill is not included throughout the training. The treadmill training session will last for 30 minutes.

Data Collection

Data will be collected 1 week before intervention and immediately after completion, and at 2 and 6 months after treatment completion. All subjects will be instructed to take their customary medications 1hour before each assessment. The assessor will be blinded to group assignment. During the baseline condition, demographic factors such as age, gender, duration of PD, and the number and daily dosage of anti-parkinsonian medications will be recorded. In each assessment session, the dosage of anti-parkinsonian medications will be recorded.

Outcome measures

Corticomotor excitability

The RMT, RC, CSP duration, SICI of the tibialis anterior muscle elicited by TMS will be used to evaluate motor cortex excitability and inhibition using the procedure described above.

Motor assessment and Functional mobility test

1. Movement Disorders Society-Unified Parkinson's Disease Rating Scale (MDS-UPDRS)

MDS- UPDRS motor scoring will be assessed for each participant a week before the TMS measure. Motor section of the MDS-UPDRS will be used. There are total of 27 items [tremor at rest (arm and leg), action tremor (arm), rigidity (arm and leg), finger taps, hand movements, rapid alternating hand movements, and leg agility]. Each item scores from 0-4, with 0 indicates no disability and 4 maximum disabled.

2. Gait and functional Performance

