All statistical analyses were performed using SPSS version 20.0 software (SPSS Inc., Chicago, IL, USA). Kolmogorov-Smirnov tests will be used to check the normality of data. One-way analysis of variance (ANOVA), Mann-Whitney U tests, and Chi-square tests will be used to compare the dependent variables (demographic data, daily dosage of levodopa, and the number of correct calculated answers/ walking time) among the 1Hz, 25Hz and sham groups. Two-way repeated measures ANOVA will be used to analyze continuous data with measurement interval (baseline, post-treatment, 2-month and 6-month post-treatment) as within-factor and group (1Hz, 25Hz, sham) as between-factor. In the case of an interaction effect between group and time being found, one-way repeated measure ANOVA and *t*-tests with Bonferroni adjustment will be used to determine the real differences. A significance level of 0.05 was employed for analysis.

5. Project Significance and Value:

The progressive and disabling features of PD are the major burden to patients themselves, their families and society as a whole. One of the most disabling motor symptoms is gait difficulty and postural instability. Beneficial long-term effects of rTMS and treadmill training suggest that this intervention could slow down motor function deterioration and maintain gait and balance performance for a relatively long period of time. To be able to walk safely and effectively will promote independence, enhance quality of life, prevent falls and reduced institutionalisation for people with PD.

References:

1. Wu T, Chan P, Hallett M. Effective connectivity of neural network in automatic movements in

Parkinson's disease. *Neuroimage* 2010;49:2581-2587

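### The 25 Hz versus 1 Hz comparison in Objectives 1 and 2 is reached only through a three-arm interaction and unspecified Bonferroni t-tests; it should be a pre-specified, baseline-adjusted contrast at each visit

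*Combined protocol and SAP*

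**What the plan says.** Project Objectives (section 2) sets two comparisons of the active frequencies: "To compare short- and long-term effects of 25Hz repetitive transcranial magnetic stimulation (rTMS) with 1Hz rTMS followed by treadmill training" for gait, and "To compare short- and long-term effects of 1Hz with 25Hz rTMS followed by treadmill training on corticomotor excitation and intracortical inhibition". The background (section 3) gives the purpose as optimising the stimulation protocol by "comparing the 2 different stimulation frequency protocols i.e. 1Hz and 25 Hz", and notes of the preceding trial: "The carry over effect has also not been examined". The visits that would answer this are set under Data Collection: "Data will be collected 1 week before intervention and immediately after completion, and at 2 and 6 months after treatment completion".

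The Statistical analysis section fits a two-way repeated-measures ANOVA with three groups (sham included) and four times (baseline included). What comes next is conditional: "In the case of an interaction effect between group and time being found, one-way repeated measure ANOVA", together with Bonferroni-adjusted t-tests. A separate sentence compares demographics, levodopa dose and a measure built from correct answers and walking time among the three groups, without that condition.

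The sample size paragraph under Participants says "The sample size calculation is based the significant findings of the gait speed and cortical silent period" and that "fifteen subjects per group are required to achieve 85% power to test the interaction effect between group and time effect".

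**The concern.** The analysis is not aimed at the stated question. A three-arm interaction asks whether any arm's course differs from any other's, so it can be significant because of sham alone. The follow-up one-way repeated-measures ANOVA has time as its only factor and cannot compare arms. That leaves the t-tests, and four things about them are open: the pairs of arms, the visits, raw or change scores, and the number of tests in the Bonferroni divisor. No step names 25 Hz versus 1 Hz, uses baseline as a covariate or calls for a confidence interval.

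Two things are at stake. If the interaction is not significant, the contrast in Objectives 1 and 2 has no planned estimate at any visit. If it is significant, the deciding test is still to be chosen, possibly after the data are seen. The 85% power also belongs to the interaction and says little about the comparison the trial was set up to make.

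**Working it through.** **Inputs.** From the documents: 3 arms, 4 times, 15 evaluable per arm, alpha 0.05, 85% power for the interaction. The documents give no SD or correlation, so I assume SD 1 at each visit, equal correlation ρ between visits (triples are ρ = 0.5/0.7/0.8), an effect constant over the three follow-ups, sphericity and two-sided t-tests. Power is per visit. Combined procedures were simulated with at least 20,000 trials per scenario.

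**1. The plan's own figure.** Dropout: 15/(1 − 0.10) = 16.7, so 17 per arm and 3 × 17 = 51; this reproduces. The 15 cannot be pinned down because the type of the 0.4 effect size is not stated. Read as Cohen's f, power at 15 per arm is:
- 98.8% with λ = f²·N·4 = 0.16 × 45 × 4 = 28.8 (ρ = 0)
- 92.9% with λ = f²(N − 3)·3 = 0.16 × 42 × 3 = 20.16
- 86.1% with the second formula and sphericity ε = 0.75

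I therefore calibrate to the stated 85%, not to 0.4.

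**2. What the interaction detects.** λ = nΣγ²/(1 − ρ), with 6 and 126 df. If one arm differs from the other two by d SD at all follow-ups, Σγ² = d² × (2/3) × (3/4) = d²/2. For d = 0.8, λ = 15 × 0.32/(1 − ρ) = 9.6/16/24, giving power of about 60/85/97%. The result is the same whichever arm stands apart. So if 25 Hz equals 1 Hz and both beat sham by 0.8 SD, the interaction is still significant in about 60/85/97% of trials.

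**3. Effect with 85% interaction power (1 Hz = sham).** This needs λ = 16.03, so d = √(16.03 × 2(1 − ρ)/15) = 1.03/0.80/0.65 SD.

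**4. Route as written at that effect.** I read it as the interaction gate plus a change-score t-test at 0.05/3. The noncentrality is d√(15/(4(1 − ρ))) = √(16.03/2) = 2.83 whatever ρ is. With 28 df the t-test alone has about 62% power; with the gate, about **59%**. With nine tests (0.05/9) it is 44%.

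**5. Baseline-adjusted contrast at that effect.** The residual variance factor is 1 − ρ², so the noncentrality is about √(16.03/(1 + ρ)) = 3.27/3.07/2.98, with 41 df. Power is about **76/70/67%** at the same 0.05/3 and **84/79/76%** with Holm over three visits. The noncentrality exceeds that of the change score by √(2/(1 + ρ)), so the gain shrinks as ρ rises.

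Other patterns, again at 85% interaction power: with sham midway between the active arms, 72% as written against 94/90/88% with ANCOVA and Holm; with 25 Hz three times as far above sham as 1 Hz, 35% against 57/50/47%.

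**6. Where the loss arises (0.8 SD, 1 Hz = sham).**

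| Procedure | ρ 0.5 | 0.7 | 0.8 |
|---|---|---|---|
| Gate + change-score t-test, 0.05/3 | 33% | 59% | 81% |
| Same, no gate | 38% | 62% | 81% |
| ANCOVA, 0.05/3 | 51% | 70% | 86% |
| ANCOVA, Holm over 3 visits | 59% | 79% | 92% |

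Before rounding, the gate costs about 5/3/1 points, the estimator 13/9/5 and the lack of step-down 8/8/6.

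**7. Effect of the unstated choices (0.8 SD, ρ = 0.7, gate kept).** 59% (change, 3 tests), 44% (change, 9), 33% (raw, 3), 18% (raw, 12).

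**8. False positives.** With no effect in any arm, the route as written gives a false 25 Hz versus 1 Hz result at any visit in about 1.7% of trials. If both active arms equally beat sham by 0.8 SD, it does so in about 4 to 5%.

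**The case against.** Much can be said for the plan. The gate is conservative and costs little. Change scores do use baseline. Part of the gain above is only Holm replacing Bonferroni: with the gate and change scores kept, Holm alone gives 39/67/87% at 0.8 SD. At ρ = 0.9 the difference nearly vanishes (98.8% as written against 99.8%). No SD or correlation is documented, so every absolute power figure is conditional. All of this stands. It limits the size of the loss but does not supply the missing specification, and the change-score, three-test reading gives the highest power of the four in step 7.

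Three stronger readings are tempting, and the documents do not support them:
- **That the plan inflates false positives.** It does not; step 8 shows the opposite. Dropping the gate and testing each visit unadjusted would be worse, at about 13 to 14% per outcome for this contrast under the null.
- **That the sample size is wrong.** The 15 per group can be reproduced under one convention. The point is only that the 85% is not the power for 25 Hz versus 1 Hz.
- **That the arms are never compared without the gate.** The measure built from correct answers and walking time is. That sentence names no pair and no visit, so it narrows the claim without closing the gap.

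Nor do the Objectives rank single-task gait above dual-task gait or the excitability measures, so a remedy should not demote any of them.

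**Conclusion.** The point holds for the repeated continuous outcomes under Objectives 1 and 2. The comparison those objectives name is neither specified nor guaranteed an estimate, and a significant interaction does not stand in for it. If the effect is the one that gives the interaction its 85% power and 1 Hz equals sham, the contrast is detected at a given visit in about 59% of trials as written. Baseline adjustment raises this to 76/70/67% at the same level, and Holm to 84/79/76%. The 59% does not depend on the assumed correlation, but it does depend on reading the t-tests as change scores with a divisor of three and on the pattern across arms. Most of the loss comes from the estimator and the multiplicity rule; the gate accounts for 1 to 5 points at 0.8 SD. This should be fixed before unblinded analysis.

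**What to change.** Replace the follow-up sentence in Statistical analysis with:

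> For each continuous outcome under Objectives 1 and 2, the 25 Hz minus 1 Hz difference is estimated at post-treatment (short term) and at 2 and 6 months (long term) by ANCOVA with three arms and the baseline value as covariate. It is reported with a 95% CI whatever the interaction shows. Within each outcome the three visits are tested with a Holm adjustment at two-sided 0.05. Comparisons with sham come from the same models, with Holm over six tests. The repeated-measures ANOVA is supportive.

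The assignment of visits to short and long term is my proposal, since the documents do not define it. Whether to name one primary outcome is a separate decision for the sponsor; like the current plan, this text does not control error across outcomes.

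In the sample size paragraph, state that the 85% refers to the three-arm interaction and not to 25 Hz versus 1 Hz. Give the power of that contrast with its assumed difference, SD and correlation.

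The cost is rewording, with no new participants or data. There are two downsides:
- The stated power for the main contrast will fall below 85% for moderate effects: about 22/33/48% at 0.5 SD with Holm.
- Per outcome, the null chance of any false 25 Hz versus 1 Hz result rises from about 1.7% to about 4.6%, and of any false result over both Holm families to about 8%. One Holm family over all nine tests holds this below 5% and still gives about 39/61/81% at 0.8 SD, against 22/44/67% for the written route at 0.05/9.

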Measures of cortical excitability including resting motor threshold (RMT), recruitment curves, intracortical inhibition (SICI) will be obtained with transcranial magnetic stimulation (TMS) for intra-rater and test-retest reliability of all these measures will be established for Study Part II. TMS assessment will be repeated twice, at least 1.5 hour apart within the same session for each study participant to assess the intra-rater reliability. Study participants will be asked to returned 1 week after for TMS assessment to assess the test-retest reliability.

Part III. Interventions

All assessment and treatment will be carried out at the electrophysiology and Gait and balance laboratory. Participants will be randomised into three groups i.e. two experimental groups and a sham group. Participants in the experimental groups will received either 1 Hz or 25Hz real rTMS and control group will receive sham rTMS, followed by treadmill training for 16 sessions over 8 weeks.

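### Holm's step-down rule could replace Bonferroni in the follow-up t-tests: for the same family it gives equal error control and about 3 to 5 points more power per contrast when one arm differs

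*Combined protocol and SAP*

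**What the plan says.** The combined protocol and SAP, section 4 (Research Methodology), under Statistical analysis, fits a two-way repeated measures ANOVA with three groups (1 Hz, 25 Hz, sham) and four times (baseline, post-treatment, 2 and 6 months). If an interaction is found, a one-way repeated measures ANOVA and t-tests follow: "tests with Bonferroni adjustment will be used to determine the real differences". On the level it adds: "A significance level of 0.05 was employed for analysis". It does not say whether the t-tests compare arms at a visit or times within an arm, or how many comparisons the Bonferroni divisor counts.

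The arms are set under Part III, Interventions: "Participants will be randomised into three groups i.e. two experimental groups and a sham group". The sample size paragraph under Participants powers only the interaction: "fifteen subjects per group are required to achieve 85% power to test the interaction effect between group and time effect". It takes 0.05 as the level and 0.4 as the effect size, without saying which kind of effect size is meant.

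**The concern.** The sample size covers the interaction test, but the objectives ask about pairs of arms, chiefly 25 Hz against 1 Hz. Those answers come from the adjusted t-tests, with about 15 evaluable patients per arm. Bonferroni holds every test to the strictest threshold, even after other hypotheses in the family have been rejected. Holm relaxes the threshold as rejections accumulate, at no cost in error control. At stake are a few points of power on the comparisons that readers will quote, and rather more on the joint claim that 25 Hz beats both 1 Hz and sham.

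**Working it through.** **1. The plan's own figures.** 15/(1 − 0.10) = 16.7, rounded up to 17 per arm, and 3 × 17 = 51, as stated ("By assuming 10% dropout rate, 17 subjects will be required per group"). The 85% depends on a convention that the plan does not name. Reading 0.4 as Cohen's f, with N = 45 and m = 4 times:
- Between-group form, correlation 0.5: λ = f²Nm/(1 + (m − 1)ρ) = 0.16 × 45 × 4/2.5 = 11.52, power 84.3%.
- Interaction form with λ = f² × error df = 0.16 × 126 = 20.16: power 92.9%.
- Standard interaction form, λ = f²Nm/(1 − ρ): about 99% or more.

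The simulation setting used below gives the interaction test about 85% power at 15 per arm, which matches the stated figure.

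**2. Why Holm is never worse.** Order the m p-values and compare them in turn with α/m, α/(m − 1), …, α, stopping at the first failure. For three tests the thresholds are 0.0167, 0.025 and 0.05; Bonferroni uses 0.0167 for all three. Suppose m₀ hypotheses are true. Before the first false rejection, at most m − m₀ hypotheses have been rejected, so the threshold at that step is at most α/m₀. The chance that any true null has p ≤ α/m₀ is at most m₀ × α/m₀ = α. As with Bonferroni, nothing is assumed about the correlation between tests.

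**3. Size, between-arm tests.** Assumptions not in the documents: unit SD, compound symmetry with correlation 0.7, 25 Hz better by 0.8 SD at all three post-baseline visits, 1 Hz = sham, two-sided t-tests on change from baseline. The interaction gate is kept. In the last column, closed testing means a 2-df arm test at the visit followed by pairwise tests at the same level.

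| 15 per arm | Bonferroni | Holm | Closed testing |
|---|---|---|---|
| 25 Hz v 1 Hz, 3 pairs at one visit | 59% | 62% | 69% (level 0.05) |
| Both 25 Hz contrasts, one visit | 45% | 52% | 62% (level 0.05) |
| 1 Hz v sham (true null) rejected, one visit | 1.6–1.8% | 3.1–3.3% | 4.6–4.8% |
| 25 Hz v 1 Hz, 3 pairs × 3 visits | 44% | 49% | 54% (level 0.05/3) |
| Family-wise error, 3 × 3 | 1.6% | 2.4–2.6% | 4.0–4.5% |

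With 20,000 trials, the standard error of a power near 59% is √(0.59 × 0.41/20,000) = 0.35 points.

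*Cross-check.* If one arm differs and f = 0.4, the difference is 0.4 × 3/√2 = 0.85 SD. The SD of change is √(2 × 0.3) = 0.775, so the noncentrality is 0.849/0.775 × √(15/2) = 3.00. The exact t-test at 0.05/3 then has 67.4% power; the simulation without the gate gave 67.9%.

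**4. Sensitivity of Holm's gain.**
- 0.85 SD, three pairs at one visit, gate kept: from 38.7% by 2.7 points (correlation 0.5) and from 66.1% by 3.3 points (correlation 0.7).
- 0.85 SD, nine tests, gate kept: 25.9% to 29.1% (correlation 0.5) and 50.4% to 56.3% (correlation 0.7).
- Graded effects (1 Hz 0.4 SD, 25 Hz 0.8 SD), one visit: 25 Hz v sham moves only from 54.9% to 55.7%, and the chance of any rejection at that visit does not change (57.4% both).

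**5. Size, within-arm tests.** Four times give 4 × 3/2 = 6 pairs in an arm. With three equal follow-up visits, Holm gains about 1 to 4 points (for example 66.5% to 70.4% at 0.7 SD, correlation 0.7), and error among the true nulls stays below 5%.

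**6. Error across visits.** The plan fixes no family, so the divisor matters. When 25 Hz differs only at 6 months, dividing by 3 separately at each visit gives 9.0–9.5% family-wise error over the three visits. Closed testing at 0.05 at each visit gives 11.7% in the sustained setting and about 13% when only 6 months differs. Holm over all nine tests (2.5–4.3%) and closed testing at 0.05/3 per visit (4.0–4.8%) stay below 5%.

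**The case against.** The case for leaving the plan alone is that Bonferroni is valid, prespecified and simple, and yields matching simultaneous intervals. Holm's gain is modest, and with graded effects it is close to nil on the largest contrast at a visit. The larger gap is that the family, the primary outcome and the primary visit are undefined. All of this stands, and it is why the point is optional. It does not alter the comparison for a fixed family: Holm is still at least as powerful at the same error, and the plan does not commit to simultaneous intervals.

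A reader might infer three stronger points that the documents do not support:

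- **That the plan wastes error whichever pairs and visits are tested.** If the divisor is 3 at each visit, error across visits already reaches 9.0–9.5%. On that reading, moving to Holm over nine tests is a tightening: power for 25 Hz v 1 Hz goes from 59% to 49%, in return for control across visits. Holm's advantage holds within a family, not between families.
- **That three arms allow unadjusted pairwise tests after the interaction.** That shortcut needs a 2-df arm test of the same contrast. The plan's gate has 6 df over all times; unadjusted t-tests behind it reach about 12% at one null visit and 21% over two. It also fails for within-arm tests, which the one-way repeated measures ANOVA may imply: unadjusted tests of the six time pairs reach 12–13%.
- **That Holm gains up to 11 points.** In the setting tabulated, Holm gains about 3 to 5 points per contrast; about 10 to 11 belongs to closed testing.

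**Conclusion.** The point holds in limited form. Whatever family the sponsor intends, Holm can replace Bonferroni with the same family-wise guarantee and no loss of rejections; this needs no assumption about data. The size does: about 3 points per contrast for three pairs at one visit, about 5 for nine tests, and about 7 for both 25 Hz contrasts together at one visit, if 25 Hz alone works with a sustained 0.8 SD effect and correlation 0.7. It falls to about 1 point on the largest contrast at one visit if effects are graded. These figures also assume between-arm tests on change from baseline, which the plan does not state. Multiplicity over the many outcomes is a separate matter. This is an optional improvement; the plan's method is not wrong.

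**What to change.** In Statistical analysis, replace the Bonferroni t-tests by: *t-tests with Holm's step-down adjustment over all follow-up comparisons of that outcome (3 arm pairs × 3 post-baseline visits = 9 for between-arm tests; all time pairs for within-arm tests).* State which kind of test is meant. If within-arm tests in all three arms form one family, it has 3 × 6 = 18 members; the within-arm figures above are for one arm.

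Optional, for between-arm tests only: at each visit, test the 2-df arm effect at 0.05/3 and, if significant, each pairwise contrast at 0.05/3 (about 54% power for 25 Hz v 1 Hz, family-wise error about 4.5%). Use 0.05 in place of 0.05/3 only if a single visit is declared the family.

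The cost is a sentence or two, no new data, and a sort of the p-values. Simultaneous intervals that match Holm or closed testing are less simple; ordinary 95% intervals can still be reported, labelled as unadjusted.

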Ten-meter walk test (10-meter walk test) and timed up and go test (TUG) were measured to evaluate the gait performance in both single task and dual task conditions. Gait parameter will be captured by the APDM systems. The APDM system is a valid, wearable gait and balance analysis system (28). The gait parameters measured includes gait speed, stride length, cadence, variability and asymmetry. Anticipatory postural adjustment, center of mass motion and postural sway path can be also measured with this system.

2.1 Single task test condition:

For 10-meter walk test, subjects will be instructed to walk at their comfortable speed and fast

walking speed from 2m before the start line of a 10m distance and complete the walk 2m after the end of 10m. Each subject will perform 3 trials for both comfortable and fast walking speed and data will be averaged.

For TUG, Subjects will be instructed to stand up from a standardized chair, walk 3m at a comfortable speed, turn around, walk back to the chair and sit down. Timing will be commenced on the word 'start' and stopped once the subject sits down again with the back touching the backrest of the chair. Each subject will perform 3 trials of TUG with one practice trial before testing commences. Timed up and go test (TUG) is a functional mobility test with good validity and reliability (29). Poor TUG performance is associated with high fall risk in PD patients (30).

2.2 Dual task test condition:

Subjects will be asked to repeat both 10-meter walk test and TUG 3 trials each while performing an additional task such as serial three subtractions (counting backwards by threes aloud).

3. Balance performance

MimiBESTest will be used to measure the balance performance. MiniBEST has been validated to identify fallers in PD (31). High inter-rater reliability and test-retest reliability were shown (32).

Statistical analysis

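### No primary outcome is named, and the group-by-time interaction is tested at 0.05 outcome by outcome with no error control across outcomes

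*Combined protocol and SAP*

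**What the plan says.** The Project Objectives section lists three numbered objectives and does not rank them. Objectives 1 and 2 are comparative; only Objective 3 (balance) is worded as exploratory.

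In the sample size paragraph under Participants, "The sample size calculation is based the significant findings of the gait speed and cortical silent period" of an earlier trial. The calculation is made "to test the interaction effect between group and time effect with a 5% significance level". Neither outcome is called primary.

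Outcome measures lists, without a hierarchy:

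- Corticomotor: "The RMT, RC, CSP duration, SICI of the tibialis anterior muscle elicited by TMS will be used to evaluate motor cortex excitability and inhibition".
- The motor section of the MDS-UPDRS.
- The 10-metre walk. For the single-task condition, "Each subject will perform 3 trials for both comfortable and fast walking speed and data will be averaged". For the dual-task condition, "Subjects will be asked to repeat both 10-meter walk test and TUG 3 trials each while performing an additional task".
- TUG, single and dual task.
- Further gait parameters: "The gait parameters measured includes gait speed, stride length, cadence, variability and asymmetry".
- The MiniBESTest.

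Statistical analysis applies a 3-group by 4-visit repeated measures ANOVA to continuous data. "In the case of an interaction effect between group and time being found", one-way repeated measures ANOVA and Bonferroni-adjusted t-tests follow. The only statement on error rate is "A significance level of 0.05 was employed for analysis".

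**The concern.** The documents do not say which test decides Objective 1 or Objective 2. The sample size paragraph narrows the field to two outcomes but does not choose between them. It also does not say whether gait speed means comfortable, fast or dual-task speed. On the natural reading, the Bonferroni step adjusts comparisons inside an outcome whose interaction has already passed at 0.05. It does nothing about the number of outcomes given that chance.

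If the plan is followed as written, a chance interaction in any one outcome can be presented as a positive result at 0.05. A reader could not tell whether that outcome was the one intended to decide the trial.

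**Working it through.** **The plan's own figure.** Dropout: 15 / (1 − 0.10) = 16.7, rounded up to 17 per group; 3 × 17 = 51. This agrees with the plan. The 15 itself cannot be confirmed, because the within-subject correlation, any sphericity correction (ε) and the effect-size convention are not stated. If 0.4 is read as a partial f, with noncentrality λ = f²(N − 3)(4 − 1)ε, the requirement is 13 per group at ε = 1 (power 92.9% at 15 per group) and 15 per group at ε = 0.75 (86.1%). So 15 is attainable. The stated 85% is taken as given below.

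**Counting outcomes.** Three sets, from narrow to broad:

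1. The two sizing outcomes: 2.
2. CSP plus comfortable, fast and dual-task gait speed: 4.
3. The plainly listed outcomes: RMT, RC, CSP and SICI (4), MDS-UPDRS motor (1), three gait speeds (3), TUG single and dual (2), MiniBESTest (1): 11. Stride length, cadence, variability and asymmetry are left out, and the recruitment curve is counted once.

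**False-positive rate.** With K independent tests at 0.05, P(at least one p<0.05) = 1 − 0.95^K:

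- K = 2: 9.75%
- K = 4: 18.5%
- K = 11: 43.1%

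Correlation lowers these. The documents give no inter-outcome correlations (r), so r is assumed. The 3 × 4 interaction test was simulated with 15 per group, F(6, 126), within-subject correlation 0.5 and no arm difference on any outcome (20,000 runs for 2 and 4 outcomes, 10,000 for 11).

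| r | 2 outcomes | 11 outcomes |
|---|---|---|
| 0 (exact) | 9.75% | 43.1% |
| 0.3 | 9.6% | 38.7% |
| 0.5 | 9.0% | 31.7% |
| 0.7 | 8.7% | 24.7% |
| 0.9 | 7.0% | 14.9% |

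Repeat simulations put the last cell of the 11-outcome column between 13.4% and 14.9%.

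For CSP plus three gait speeds:

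| r among speeds | CSP uncorrelated with speeds | CSP correlated 0.3 with speeds |
|---|---|---|
| 0.5 | 17.1% | 16.9% |
| 0.7 | 16.1% | 15.3% |
| 0.9 | 13.2% | 13.4% |

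These rates concern any difference among the three arms, including differences from sham. They are not rates of falsely claiming that 25 Hz beats 1 Hz.

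**What the remedies do, for two outcomes.** Simulated error at r = 0 / 0.5 / 0.9 is 5.2 / 5.1 / 4.8% with gating and 5.0 / 4.7 / 3.7% with a 0.025 split or Holm.

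Power: with F(6, 126), 85% at 0.05 corresponds to λ = 16.03, and the same λ gives 77.2% at 0.025. From this:

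- Gated, first outcome: 85%. Second outcome, both effects real and independent: 0.85² = 72%; simulated 76% at r 0.5 and 80% at r 0.9.
- Gated, first outcome truly null and independent: 0.05 × 0.85 ≈ 4% chance of claiming the second.
- Split at 0.025: 77% each.
- Holm, both effects real and independent: 0.772 + (0.850 − 0.772) × 0.772 = 83% each; simulated 81% at r 0.9.
- Holm, only one effect real, independent: 0.772 + 0.078 × 0.025 = 77%.

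**The case against.** The plan has more structure than a flat list. Its two sizing outcomes match Objectives 1 and 2 one to one, and Objective 3 is exploratory. Whether two separately stated objectives need joint error control is debated. If each supports its own claim, 0.05 per objective is defensible, and the 7–10% figure is then not a fault. That argument stands. It does not say which gait speed decides Objective 1 or which of four corticomotor measures decides Objective 2. Even within one objective, the rate is up to 1 − 0.95³ = 14.3% for three speeds and 1 − 0.95⁴ = 18.5% for four corticomotor measures. Both are upper ends at independence.

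The 11-outcome count and the correlations are assumptions, and 43% needs independence, which is unlikely for walking measures on the same person. This also stands. A block structure (0.3 among TMS measures, 0.7 among motor, gait and balance measures, 0.1 between blocks) gives about 33%, so the mid-range near 32% is the fairer summary.

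The plan says continuous data, not every outcome, and sends a few measures to other tests. It states no success rule, so how a lone positive interaction would be reported is inferred. These points soften the wording of the concern but not its substance.

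**Conclusion.** The concern holds. No outcome is designated primary, and no rule controls error across outcomes. The most relevant size is about 13–17%, the rate for CSP plus the three measured gait speeds, because it stays within what the sample size paragraph singles out. It rises to about 32% across 11 listed outcomes at r 0.5, with a range of roughly 13–43% over r 0.9 to 0. Testing further gait parameters would raise it. All of these rest on assumed correlations and on no true difference in any outcome; only the independence values are exact. The gap should be closed, but the planned data remain usable and the design need not change.

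**What to change.** Before unblinding, name one primary outcome drawn from the two sizing outcomes, together with its deciding test. If it is gait speed, state the version. One example, which the text does not dictate, is single-task comfortable-speed gait speed on the 10-metre walk. It would be tested at 0.05 with the planned 3 × 4 interaction, followed by the planned Bonferroni pairwise comparisons. Dual-task speed would also be defensible, since Objective 1 names both conditions. Because the interaction responds to any arm difference, the follow-up must include 25 Hz versus 1 Hz and state its time points and number of comparisons. For instance, three arm pairs at three post-treatment visits would be nine.

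Then choose one of:

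- **(a) Gating:** test the other sizing outcome at 0.05 only if the primary is significant.
- **(b) Co-equal outcomes**, if Objectives 1 and 2 rank equally: test each at 0.025, or use Holm (smaller p at 0.025, then the other at 0.05).

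Report all other outcomes, including the gait-speed versions not chosen, as secondary or exploratory estimates with 95% CIs.

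The cost is SAP wording, with no new visits or participants, and the other outcomes lose confirmatory status. Gating protects the first outcome's power at the expense of the second. The split leaves each outcome below the planned 85%, and Holm recovers most of that when both effects are real. Restoring 85% at 0.025 would take 17 per group before dropout under the partial-f, ε = 0.75 reading, or 17 / 0.9 = 18.9, so 19 recruited per group. If the sample stays at 51, the SAP should state the lower power.
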